13.10 Extended follow up phase

The participant's clinical records should be reviewed at 60 and 72 months after the date of CRCLM surgery/randomisation for participants who have consented to extended follow-up to collect any evidence of disease progression or a new primary cancer.

13.11 End of follow up phase/Trial

The participant's clinical records should be reviewed at 84 months after the date of CRCLM surgery/randomisation for participants who have consented to extended follow-up in order to collect any evidence of disease progression or a new primary cancer. This will be the last assessment for participants reaching this time point.

13.12 Disease Progression

The date of clinical progression is defined as the **date of the CT scan or the relevant assessment at** which disease progression or new recurrence is identified. This can be clinical progression or, for RECIST evaluable disease, radiological progression by RECIST principles.

In the event that the liver or extra-hepatic metastases are found to be unable to be resected following randomisation (macroscopic disease remaining), a CT scan to determine the existing disease should be carried out as soon as possible following surgery. This scan will act as a baseline for assessment of progression and should be reported in accordance with RECIST v1.1⁵⁸ (see Appendix D). Subsequent scans to monitor disease progression should also be reported in accordance with RECIST v1.1.

Up to 5 target lesions should be defined. Disease progression is defined as:

- Appearance of one or more new lesions
- A minimum 20% increase in the sum of diameters of target lesions. In addition to the relative increase of 20%, the sum must also demonstrate an absolute increase of at least 5 mm.
- Clear, unequivocal progression of non-target lesions (which may be measurable or non-measurable)

In the event that a participant is found to have positive microscopic margins following liver resection (microscopic disease) an immediate CT scan is not required as this disease is not evaluable according to RECIST. Disease progression is defined as the appearance of CRC metastases by CT scan of the thorax/abdomen/pelvis.

Disease progression in the extra-hepatic metastases will be assessed using the CT scan of the thorax/abdomen/pelvis if appropriate. Other clinical evaluations will be carried out to monitor extra-hepatic metastases as required and as per local standard practice.

In a small number of cases, participants may have clear clinical symptoms of disease progression without confirmatory imaging. In this circumstance, clinical deterioration that is unambiguously due to CRC progression should be reported as a progression event and the date of clinical assessment should be recorded as the date of clinical progression.

13.13 Quality of Life

For all participants, Quality of Life (QoL) questionnaires will be completed at visit 1, visit 3 and at all clinic visits thereafter. The QoL questionnaires include the EQ-5D, EORTC QLQ-C30 and QLQ-LMC21 questionnaires.

13.12.1. Timing and administration of Quality of Life questionnaires

Participants will be asked to complete the Quality of Life questionnaires prior to receiving their first box of capsules and wherever possible prior to meeting with the clinician at the clinic visit (or prior to randomisation at visit 1). The Visit 1 Questionnaire Pack should be given to participants after consent has been obtained and eligibility has been confirmed. All questionnaires will be provided in clinic or by post.

Questionnaires should be completed by participants at the time of clinical assessment, but before discussion of the outcome of any medical assessments or blood tests wherever possible. Participants will be asked to seal the questionnaires in pre-supplied envelopes prior to being given to research staff. Research staff will then send the sealed envelopes to the CTRU for entry into the database.

13.14 Health Economics

For all participants, a health economics questionnaire will be completed at all clinic visits.

13.15 Cachexia CT measurements

Changes in lean body mass will be measured longitudinally from the routine CT abdomen images from participants in Leeds and Sheffield using the method of Baracos (based on muscle area at the L3 vertebral level⁴⁴). The routine CT scans will be obtained at baseline (confirmation of eligibility), visit 3 and visit 4. The CT scan images will be requested at the end of the interventional phase, depending on the availability of funding for measurement of this exploratory endpoint. These measurements could easily be extended to cover longer periods of follow-up or expanded to include participants at other sites if funding is available.

It is the responsibility of the participating centre to obliterate all personal identifiable data prior to sending the CT scan to the CTRU/central reviewer. The trial number, date of birth and initials will be used to identify the participant.

13.16 Red Blood Cell Fatty Acid Analysis

Blood samples taken at visits 1, 2 and 3 will be collected from participants recruited at two of the participating centres: Sheffield Teaching Hospitals NHS Foundation Trust and Leeds Teaching Hospitals NHS Trust. These samples will be analysed to measure the red blood cell fatty acid content which determines the absolute and relative content of the major O3FAs including EPA, as well as the EPA/AA and EPA+DHA/AA ratio⁵².

The fatty acid analysis on the baseline samples (see Section 13.2) will enable the investigation of whether O3FA status predicts subsequent therapeutic response to IPE. The absolute and differential O3FA levels at visits 2 and 3 will also act as a marker of compliance to IPE and allows the assessment of whether the placebo arm has been 'contaminated' by possible participant supplementation with over-the-counter O3FA.

At visits 1-3, whole blood will be collected in EDTA tubes for centrifugation and isolation of plasma and red blood cells. Both fractions will be stored locally at -30°C before courier transport of the complete sample sets to the Institute of Cancer Therapeutics (ICT), University of Bradford which will act as the central biobank. Lipid extraction from red blood cells followed by derivatisation and liquid chromatography-tandem mass spectrometry (LC-MS/MS) measurement of individual fatty acid (FA) species will be performed as described in the EMT2 Lab Manual⁵².

The red blood cell fatty acid analysis will be carried out centrally at the Institute of Cancer Therapeutics (ICT), University of Bradford.

The fatty acid analysis will be carried out on blood samples from all participants recruited at Sheffield Teaching Hospitals NHS Foundation Trust and Leeds Teaching Hospitals NHS Trust only.

At visits 1-3, whole blood will be collected for centrifugation and isolation of plasma and red blood cells. Blood samples will be obtained using the BD Vacutainer® system, following local Trust practice. Two purple cap K₂EDTA 6ml tubes will be filled to capacity. Tubes should be agitated immediately to prevent clotting.

The blood components should be separated within 30 minutes of taking the blood sample. If not processed immediately, the two K₂EDTA Vacutainer tubes should be stored in the fridge at 4°C for up to 30 minutes.

Separation of blood components will be achieved by centrifugation of the sample in K₂EDTA Vacutainers in a centrifuge, preferably refrigerated.

Full details on the separation of the blood components are provided in the EMT2 Lab Manual.

All separated fractions will be stored locally at -30°C before courier transport of the complete sample sets to the ICT, Bradford every three months. Lipid extraction from red blood cells

followed by derivatisation and liquid chromatography-tandem mass spectrometry (LC-MS/MS) measurement of individual FA species will be performed as described in the EMT2 Lab Manual.

The fatty acid-analysis may be carried out at intervals during the two years of recruitment in order to assess treatment compliance and/or 'contamination' by 'over-the-counter' O3FA use.

Any blood samples remaining following analysis for trial purposes will be stored at the Institute of Cancer Therapeutics at the University of Bradford and may provide a resource for future studies in colorectal cancer. Ethical approval will be obtained for any future studies involving EMT2 data or samples and the Institute of Cancer Therapeutics at the University of Bradford has been granted a main HTA licence (12191). Participants will not be identified in the results of future studies.

It is the responsibility of the participating centre to ensure that samples are appropriately labelled in accordance with the trial procedures to conform with the 1998 Data Protection Act. Blood samples collected from participants as part of this study will be transported, stored, accessed and processed in accordance with national legislation relating to the use and storage of human tissue for research purposes and such activities shall at least meet the requirements as set out in the 2004 Human Tissue Act.

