PIS/ICF	Participant Information Sheet and Informed Consent Form
QALY	Quality adjusted life year
RCT	Randomised controlled trial
RN	Research nurse
SAE	Serious adverse event
SAR	Serious adverse reaction
SmPC	Summary of Product Characteristics
SUSAR	Suspected unexpected serious adverse reaction
TG	triglyceride
TMG	Trial Management Group
TSC	Trial Steering Committee

Term	Definition
Kit-code	Unique numerical identifier used to identify the IMP boxes without revealing the treatment allocation.
Replenishment	A repeat allocation of trial IMP via the CTRU 24-hr automated system.
Replacement	A repeat allocation of trial IMP via the 24-hr automated system which takes place at an unscheduled time point.
Safety Statistician	An independent CTRU statistician responsible for undertaking tasks that require knowledge of the treatment allocation.
Authorised Unblind Individual (AUI)	A member of CTRU staff who is permitted to have knowledge of treatment allocation but is not part of the trial team or the safety statistician. The individual is authorised to perform tasks and processes where knowledge of treatment allocation is required. This ensures the blind is not compromised for the blinded members of the team. A trial may have multiple people designated as AUI.

6. Background

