6.5 The IMP in EMT2

Icosapent ethyl (IPE) or Vazkepa®, also known as AMR101 or Vascepa® in the USA, (Amarin Pharmaceuticals Inc.), is approved by the Medicines and Healthcare Products Regulatory Agency (MHRA), European Medicines Agency (EMA) and US Federal Drug Administration (FDA) for prevention of cardiovascular events in individuals with established cardiovascular disease, or diabetes and at least one other cardiovascular risk factor, who are already taking a statin and have elevated blood triglyceride levels at a dose of 4 g per day. It is available as 1 g (998 mg) EPA-EE in soft gelatin capsules. Therefore, each capsule contains the equivalent of 914 mg EPA-FFA. Dosing is recommended with meals. Pharmacokinetic studies have demonstrated a dose-response relationship with the plasma and red blood cell EPA level attained (and changes in other red blood cell O3FAs), with IPE 4 g/day providing a significant increase in plasma and red blood cell EPA level after 12 weeks therapy compared with 2 g/day⁴⁸. Plasma EPA levels (expressed as the % total fatty acids) in patients with hypertriglyceridaemia after 12 weeks treatment with 2 g/day and 4 g/day were 1.9% and 3.4-3.6% respectively⁴⁸⁻⁴⁹. An 8-week study in healthy volunteers of EPA FFA 2 g daily (used in EMT²⁷ and seAFOod²⁵ trials) resulted in plasma EPA levels of 4.6%⁵⁰. Treatment with EPA FFA 2 g daily for a shorter period (median 30 days) in the EMT trial (which may not have generated steady-state O3FA levels) was associated with a similar % increase in red blood cell EPA content (240%)²⁷ to that seen with IPE 2 g/day for 12 weeks (300%; cf. 500% with 4 g/day)⁴⁸. In a Japanese trial of 1800 mg EPA-EE per day for 5 years, the % change from baseline of serum EPA (as the % of total fatty acids) was only 126%⁵¹. Therefore, the available evidence suggests that dosing with 4 g/day IPE will produce EPA bioavailability most similar to that obtained with EPA-FFA and EPA-TG in previous CRC trials⁵² with the caveats that there has been no direct comparison between different EPA formulations in CRC patients and that

differences in methodology for measurement and reporting of plasma, serum and red blood cell EPA content mean that direct comparisons should be carried out cautiously.

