12.3 Blinding

The Principal Investigator, participating centre staff, pharmacy staff, participants and the CTRU staff involved in the day to day activities of the trial will be blinded to the treatment allocation of each participant.

Participants will not be informed of their trial allocation until the final analysis has been completed and the results of the study are published. At this time the CTRU will provide each site with a list of treatment allocations for participants recruited at that site. Participants cannot request their trial allocations until this time.

The following controls will be employed to maintain the double blind status of the trial:

- The IPE and placebo capsules and bottles will be identical in appearance and have the same labelling.
- Boxes will be identified by a unique kit code assigned at random. The CTRU Safety Statistician (an independent CTRU statistician responsible for carrying out tasks requiring access to unblinded information) will be responsible for maintaining this list, which will be securely password protected when treatment information is contained within the list.
- The Investigator and other members of the site staff involved with the trial and the participants themselves will remain blinded to the treatment allocation (except where emergency unblinding is necessitated).

The following outlines how unblinding will be kept to a minimum for tasks to be conducted unblinded at the CTRU:

- Management of kit-codes on the kit logistics application which is linked to the 24-hour randomisation system will be conducted by the CTRU Safety Statistician in addition to maintaining the back-up kit-code lists for each centre.
- Any unblinded interim reports provided to the Data Monitoring and Ethics Committee (DMEC) will be provided by the CTRU Safety Statistician and the reports will be securely password-protected.
- Suspected Unexpected Serious Adverse Reactions (SUSARs) will be unblinded by the CTRU Safety Statistician. If the event requires expedited reporting, the Safety Statistician will pass the SUSAR to the trial Data Manager who will be responsible for electronic SUSAR reporting to the Medicine and Healthcare Regulatory Agency (MHRA) and the ethics committee. Unblinded records of SUSARs reported will be maintained by the Safety Statistician.

Code break procedures are outlined below and described in detail in the Emergency Unblinding SSOP provided in the Investigator Site File and Pharmacy Site File.

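### Section 12.3 blinds day-to-day CTRU staff yet routes unblinded SUSARs to the trial Data Manager; Section 13.16 permits allocation-revealing assays without saying who may see the results

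*Protocol*

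**What the plan says.** **SUSARs.** Protocol Section 12.3 sets the general rule that "CTRU staff involved in the day to day activities of the trial will be blinded to the treatment allocation of each participant". Under the tasks to be done unblinded it then states: "Suspected Unexpected Serious Adverse Reactions (SUSARs) will be unblinded by the CTRU Safety Statistician". If a case needs expedited reporting, "the Safety Statistician will pass the SUSAR to the trial Data Manager who will be responsible for electronic SUSAR reporting". It adds: "Unblinded records of SUSARs reported will be maintained by the Safety Statistician".

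The glossary in Section 5 defines an Authorised Unblind Individual, a CTRU staff member who is neither in the trial team nor the Safety Statistician. Of this role it says: "The individual is authorised to perform tasks and processes where knowledge of treatment allocation is required". The stated purpose is to protect the blind of the rest of the team.

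**Fatty-acid assays.** Section 13.16 provides for red-cell fatty-acid measurement at visits 1 to 3 in Leeds and Sheffield participants, at a central laboratory in Bradford. On timing it says: "The fatty acid-analysis may be carried out at intervals during the two years of recruitment in order to assess treatment compliance". Contamination by over-the-counter omega-3 use is given as a further purpose, and the same section refers specifically to contamination of the placebo arm. The tasks that Section 12.3 lists as done unblinded are kit-code management, DMEC reports and SUSARs. The assays are not among them.

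**The concern.** The trial relies on its blind. PFS is assessed locally, and Section 13.12 allows clinical deterioration without confirmatory imaging to count as progression. CTRU data staff query sites about missing and discrepant data (Sections 13.24 and 20.2). A person who handles those queries should not know any participant's arm, yet the SUSAR route in Section 12.3 gives that knowledge to someone who appears to belong to the blinded group.

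The assay raises a different and weaker issue. The protocol permits, during the trial, a measurement that comes close to reading out allocation, for purposes that only make sense when results are read by arm. It does not say who may see the individual values.

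**Working it through.** The plan states no figure on this point that could be reproduced. The SUSAR part is a comparison of sections. The assay part needs a short calculation.

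**SUSAR route**

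1. Is the Data Manager in the blinded group? Section 12.3 does not name the post. Section 25.1 places data management and safety reporting within the CTRU's day-to-day running of the trial, so the post fits the group that Section 12.3 blinds.
2. What does the Data Manager learn? Section 12.3 puts unblinding first and the hand-over second, and only cases needing expedited reporting are handed over. Section 14.2.2.3 says that events associated with placebo will usually not meet the SUSAR criteria.
3. Selection after unblinding is therefore informative. A case that is passed on was most likely on IPE, whether or not the form shows the arm. Keeping the unblinded records with the Safety Statistician does not remove that signal.
4. A role that avoids the problem is already defined in Section 5. The visible text of Sections 12.3 and 14 does not use it for SUSARs.

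**How revealing an individual assay result would be**

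Inputs from the protocol:
- Rise in red-cell EPA (Section 6.5): 240% in the Phase II trial (EPA-FFA 2 g daily, median 30 days). For IPE at 2 g/day and 4 g/day over 12 weeks the figures are "300%; cf. 500% with 4 g/day".
- Between-patient CV of about 10% (Section 6.2). This is quoted for omega-3 levels in general, not for EPA alone.

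Assumptions: the ratio of follow-up to baseline is log-normal; the placebo ratio is 1 and the active ratio is 1 + r, where r is the rise; the two measurements are independent; the guess is made at the midpoint on the log scale. Then

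s = √(2·ln(1 + CV²)) and P(correct guess) = Φ( ln(1 + r) / (2s) ).

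Example at CV 10%, r = 2.4: s = √(2 × ln 1.01) = 0.141; ln 3.4 = 1.224; 1.224 / 0.282 = 4.34; P ≈ 1.00.

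Example at CV 50%, r = 5: s = √(2 × ln 1.25) = 0.668; ln 6 = 1.792; 1.792 / 1.336 = 1.34; P = 0.91.

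| CV | rise 240% | rise 300% | rise 500% |
|---|---|---|---|
| 10% (Section 6.2) | 1.00 | 1.00 | 1.00 |
| 20% (assumed) | 0.986 | 0.993 | 0.999 |
| 30% (assumed) | 0.930 | 0.953 | 0.985 |
| 50% (assumed) | 0.820 | 0.850 | 0.910 |
| 30%, half the rise (both assumed) | 0.83 | 0.87 | 0.93 |

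The last row allows for partial adherence, or for a visit 2 sample taken soon after randomisation. A blind guess would score 0.50.

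**Length of the window.** Section 13.16 still speaks of two years of recruitment. Section 18.1 now gives 67 months, which is 67 / 24 = 2.8 times as long.

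**The case against.** **On SUSARs.** The hand-over sits in a list meant to keep unblinding to a minimum, so it can be read as a disclosed, limited exception. The text does not say that the allocation travels with the case, and SUSARs should be few. What stands of this is the small scale. The conflict remains, because a disclosed exception that reaches the blinded team is still an exception to the rule in the same section, and selection for reporting carries the signal by itself.

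A reader might also infer that no procedure in the trial uses the Authorised Unblind Individual. That cannot be established. The Appendix B flowchart is not visible and the Emergency Unblinding SSOP is a separate document, so the statement is limited to the text shown.

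**On the assays.** A reader might infer that Section 13.16 delivers allocation-revealing results to blinded staff. The protocol does not say so. The analysis is optional, central and limited to two sites, and no recipient is named. The general rule in Section 12.3 covers these results in principle. The glossary gives the Safety Statistician the tasks that need knowledge of the arm, and Section 20.1 sends unblinded reports to a closed DMEC session. The Lab Manual and the data monitoring analysis plan, neither shown, may hold the data flow. All of this stands, and it makes this part a gap in explicit control rather than a stated breach.

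A reader might take 128 of 388 participants (33%) as the share exposed. That is not an exposure figure. In Section 18.1.1, 128 is the number needed for the muscle-mass comparison, not a count of blood samples, and Section 13.5 excuses remotely followed participants from the visit 3 sample.

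**On bias.** Progression is identified and dated at sites, and neither procedure is shown to carry allocation there. Section 14.4.3 has the CTRU notify investigators of SUSARs, but does not say what the notice contains, so it cannot be counted either way.

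**Conclusion.** The SUSAR point holds as an internal contradiction in Section 12.3. It rests on two inferences: that the trial Data Manager is day-to-day staff, which Section 25.1 supports, and that receipt of a reportable case implies IPE, which Section 14.2.2.3 supports.

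The assay point is secondary. Individual post-baseline values would usually reveal the arm: close to certainty at the protocol's CV, and 82% to 91% at an assumed CV of 50%. The protocol permits such assays during recruitment without saying who may see these values. It does not route them to blinded staff, and the general blinding rule gives partial cover.

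The likely effect on the PFS comparison is small. The case for acting is that the correction is specific, nearly free and removes a conflict written into the blinding section itself.

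**What to change.** 1. **Section 12.3, SUSARs.** Assign electronic submission of unblinded SUSARs to the Authorised Unblind Individual or the Safety Statistician instead of the trial Data Manager. Check that Appendix B agrees.
2. **Sections 12.3 and 13.16, assays.** State that participant-level post-baseline fatty-acid results go only to the Safety Statistician until database lock, and that arm-level summaries of compliance and contamination go to the DMEC closed session. Add this task to the list in Section 12.3 of work done unblinded.
3. **Section 13.16, timing.** Bring the reference to two years of recruitment into line with the 67 months in Section 18.1.

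The cost is a few wording changes and a data-flow instruction to the central laboratory. The roles already exist. The one real drawback is that the trial team must wait until database lock for individual EPA results.
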